4.0 Study Intervention

4.1 The comprehensive trauma-based reentry program has two primary components: a trauma-based intervention paired with community stabilization reentry efforts. Consistent with evidence-based reentry approaches,⁶⁶ the proposed intervention will use trauma-trained reentry practitioners to deliver the intervention and provide reentry supports including coordinating substance abuse treatment, assisting with housing, and providing employment services.

Trauma-Based Intervention Component. Trauma Affect Regulation: Guide for Education and Therapy (TARGET) is a manualized, cognitive-behavioral, trauma-based group program designed for both young men and young women with a history of LTEs who are experiencing trauma symptoms. TARGET has an established evidence base.⁶⁷⁻⁷¹ Up to fourteen TARGET sessions will be paired with the specialized reentry supports. Up to four sessions will occur prior to release and up to ten sessions will be delivered in the community post-release.

TARGET helps participants understand and manage trauma memories and affective dysregulation and provides psychoeducation and skills-based learning on how to process and manage trauma-related reactions to stressful life situations, including PTSD symptoms, traumatic grief, and shame. The goal of TARGET is to increase emotional regulation and coping, helping participants gain control of intense emotions and posttraumatic stress reactions while simultaneously solving daily stressors and maintaining sobriety. Like other present-focused, cognitive-behavioral interventions, TARGET provides a systematic approach to processing trauma that does not require memory processing or risk re-traumatization. The comprehensive trauma-based reentry program pairs trauma-based components with community stabilization reentry efforts. Consistent with evidence-based reentry approaches, the proposed intervention will use trauma trained reentry specialists to deliver the intervention and provide reentry supports to help improve community stabilization.

The comprehensive trauma-based intervention component will be delivered across up to 19 sessions and each session will simultaneously include a focus reentry planning, community stabilization, and trauma treatment. Up to four sessions will take place in prison before release and up to 15 sessions will take place in the community upon release from prison. Sessions delivered during custody will provide psychoeducational information on trauma and reentry, and facilitate reentry planning with a focus on community stabilization and service identification and access. Sessions in the community will be delivered post-release and will focus on emotion awareness and regulation, recognizing and

positively responding to their triggers, evaluating their thoughts, and identifying positive emotions. Post-release sessions will also enable the participants to develop healthier coping skills, manage their mental health symptoms, impulsivity, and aggression, and decrease substance abuse.

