Title: Researching Resiliency in Stressful Experiences (RISE) Program for Men Leaving Incarceration

NCT #: NCT04785677

Date: 4/14/2020

Study Summary

Study Title	Multisite Randomized Controlled Trial of Comprehensive Trauma Informed Reentry Services for Moderate to High Risk Youth Releasing From State Prisons
Study Design	1:1 Randomized Control Trial
Primary Objective	Determine whether the TARGET program helps young men released from prison improve their mechanisms of change.
Secondary Objective(s)	Determine whether the TARGET program helps young men released from prison improve their community stability and decrease their odds of recidivating.
Research Intervention(s)	Trauma Affect Regulation: Guide for Education and Therapy (TARGET)
Study Population	Incarcerated men aged 18-35 who have experienced at least one traumatic event in their lifetime. .
Sample Size	400
Study Duration for individual participants	Up to 18 Months
Study Specific Abbreviations/ Definitions	Lifetime Traumatic Events (LTE), Trauma Affect Regulation: Guide for Education and Therapy (TARGET), Department of Corrections (DOC).

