Across samples and study design, 62-98% of incarcerated males report at least one LTE (prior to incarceration)¹⁴⁻¹⁶ compared to 22-47% of men who have never experienced incarceration.^{17,18} Specifically, 58% of incarcerated males report physical abuse and 17% report sexual abuse in childhood - 2-3 times the estimated prevalence among males in community-based samples.¹⁹⁻²¹ Further, while discussions about LTEs typically center on the experiences of women and girls, incarcerated and formerly incarcerated males and females report equally high numbers of LTEs, although the nature of LTEs differ between the genders. Although incarcerated females report 2.5-4 times the rate of sexual abuse/assault as incarcerated males, incarcerated males report witnessing extreme harm to others at nearly double the rate as incarcerated females (60% vs. 34.8%).²² Incarcerated males also report interpersonal nonsexual trauma in adolescence at nearly twice the rate as incarcerated females (63.2% vs. 34.8%).²²

Addressing LTEs among incarcerated males is important because more than 95% of those who are incarcerated are eventually released²³ and trauma symptoms and risks for recidivism are correlated. Trauma symptoms include increased sensitivity to stress, high levels of negative emotionality, sensation seeking (i.e., pursuing risky, stimulating experiences),^{24,25} aggression, impulsivity, dissociation, impaired ability to adequately assess risk, and unrealistic expectations of interpersonal relationships.²⁶⁻²⁸ Rates of posttraumatic stress disorder (PTSD) are higher among males with incarceration histories (21%) when compared to both males in the general population (4%-5%) and male veterans (7%)^{16,21,29,30}; incarcerated males with substance use disorders are 80% more likely to have experienced two or more LTEs³¹ including previous physical or sexual assault.¹² These individuals struggle to remain abstinent from drugs and alcohol after release from incarceration^{12,32,33} and are more likely to be re-arrested when compared to their non-victimized peers.^{10,34,35}

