5.3 Research team members have experience working with people with trauma histories. This is important so they can successfully assess if there are adverse behaviors or thoughts during service delivery (treatment group) and during data collection interviews (all participants). All interviews are conducted one-on-one so the research team member can assess for adverse reaction to the data collection or treatment delivery.

6.4 Data will be collected from participants during one-on-one interviews. Interviews will occur in a private space, where the conversation between the team member and individual cannot be

heard. Data will be recorded in RedCap computer software. Potential participants will complete 12 -count trauma checklist as a screener for assessing for presence of at least one LTE. Eligible participants will plan to release to one of our four Florida counties. Participants will be consented using a Florida State University IRB consent form. If the individual meets screening criteria and consents into the study, the research team member will complete the baseline interview.

All consented participants (treatment and control) will complete a series of interviews. Baseline interviews will occur immediately after consent and occur in prisons. Follow-up interviews will be conducted in the community and timepoints include (1) after the conclusion of the program period, (2) three months after the conclusion of the program period, and (3) nine months after the conclusion of the program period.

6.5 Measures were selected based on the quality of established psychometric evidence and use with criminal justice-involved or other at-risk populations.

- Risk Assessment. Spectrum is the assessment tool used by FDC that identifies risk factors for criminal behavior. Scores on Spectrum range 1-5. The assessment is given to individuals at intake, periodically throughout incarceration and then again under a year before they release and measures an individual's risk to recidivate.
- Trauma screener. A dichotomous Yes/No measure of 12 LTEs from the Trauma Assessment for Adults serves as the trauma screening tool. Participants are identified as eligible if they have experienced at least one LTE.
- Demographics. Age, race/ethnicity, marital status, level of education at release, age at first offense, number of prior incarcerations, most serious offense, and current sentence length will be collected from FDC administrative databases.

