9.0 Subject Population*

Commented [A1]: Eligibility : Age, Risk Factor Identification (spectrum?), Screening for Lifetime Traumatic Experiences, Conversational English, Cognitive Consent, Release to Leon or Duval

Random Number generator (randomization)

9.1 Participant inclusion requirements include: (1) male; (2) age 18-35; (3) identified as having risk for recidivism; (4) screened as experiencing at least one LTE; (4) releasing from incarceration to one of our four study counties within six months; (5) conversational English; and (6) being able to cognitively consent into study participation.

9.2 Participants may be excluded if: they (1) identify as women; (2) younger than 18 or older than 35; (3) no demonstrated any risk; (4) not cognitively able to understand what it entails to be a research participant.

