Title: Researching Resiliency in Stressful Experiences (RISE) Program for Men Leaving Incarceration

NCT #: NCT04785677

Date: 4/14/2020

Analytic Plan. STATA version 14 will be used for data cleaning, coding, and analysis.

Prior to analysis, data will be examined for missing and outlier values to resolve any issues.

Descriptive statistics will be computed for each variable. Correlation matrices and squared multiple correlations will be examined for multicollinearity and singularity. The reliability of scales composed of multiple items will be assessed. Precautions will be taken to minimize the amount of missing data (i.e., robust methods of participant tracking and incentives to participate). If missing data occurs, analyses will be undertaken to test for the assumption of missing at random (MAR) or missing completely at random (MCAR). Based on the determined pattern and proportion of the missing data, the recommended procedures for multiple imputation may be performed. Multivariate statistical methods must meet multiple assumptions before analyses can occur. We will test for the following assumptions: normality, multicollinearity, homoscedasticity, independence of error terms, and linearity. If assumptions are not met, appropriate corrections and transformations will be made.

Key Mechanisms of Change and Community Stability. We will use the multivariate statistical test of Analysis of Covariance (ANCOVA) to test our study aims around key mechanisms of change (i.e., trauma symptoms, coping, impulsivity, and aggression) and community stability (i.e., housing and employment). One two-level independent variable indicates the study condition: the comprehensive trauma-based reentry program condition and the TAU control condition. ANCOVA allows for an assessment of between-group differences on key mechanisms of change and community stability after controlling for the effects of one or more covariates (e.g., race, other program participation, criminal history). The purpose of this analysis is to partial-out the effects of study condition on key mechanisms of change and community stability, determining whether any effects are due to the covariates and/or are a result of the study condition assignment.

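### TARGET is described as a program for people with current trauma symptoms, but men are enrolled on exposure alone, and the SAP neither names baseline symptoms as a covariate nor estimates whether the effect depends on them

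*Protocol*

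**What the plan says.** Protocol section 4.1 presents TARGET as a "group program designed for both young men and young women with a history of LTEs who are experiencing trauma symptoms". That sets two conditions: past exposure and current symptoms.

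Eligibility uses only the first. The Study Summary gives the population as "Incarcerated men aged 18-35 who have experienced at least one traumatic event in their lifetime". The trauma screener in section 5.0 (item 6.5) is a 12-item yes/no list: "Participants are identified as eligible if they have experienced at least one LTE". Section 9.1 repeats the exposure criterion. Its other criteria are sex, age, recidivism risk, county of release, English and capacity to consent.

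Section 2.0 reports that "62-98% of incarcerated males report at least one LTE" and puts PTSD at 21% among men with incarceration histories.

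For the mechanisms of change, the SAP plans an ANCOVA: "One two-level independent variable indicates the study condition". Its example covariates are race, other program participation and criminal history. No baseline symptom score is named, and no interaction or subgroup is planned. Section 5.0 has the PCL-5 and the other mechanism measures taken at every interview, including the baseline interview in prison. Scores above 33 on the PCL-5 are read as current PTSD.

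**The concern.** The primary objective is improvement in the mechanisms of change, and PTSD symptoms are one of them. If many enrolled men start with low PCL-5 scores, they have limited room to fall further. The average arm difference could then be small even if the program works well in men with substantial symptoms, the group section 4.1 describes.

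With one pooled effect and no planned use of baseline symptoms, a null PCL-5 result would have two readings: the program does not work, or it works mainly in men who start with symptoms. Nothing prespecified would help to separate them, and an analysis added after a null result would be post hoc. The data needed are already being collected.

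**Working it through.** **1. The plan's sample size.** The SAP gives 352 for two groups, up to seven covariates, alpha .05, power .80 and an effect labelled Cohen's d = .15. Using the noncentral F with 1 numerator df, N - 9 denominator df and noncentrality N × f²:
- .15 entered as Cohen's f (equivalent to d = 0.30): N = 351, power .80 at 352 and .85 at 400. This reproduces the plan's figure.
- .15 as d (f = .075): N = 1,398, power .32 at 400. This does not.

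The label is a separate matter. Below, d = 0.30 is used because it is the effect that 352 corresponds to.

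**2. Share of enrolled men with PTSD.** Assume every man with PTSD reports at least one LTE. The share is then 0.21 / (LTE prevalence).
- LTE 62%: 0.21/0.62 = 33.9%, about 135 of 400; 66.1% without PTSD.
- LTE 98%: 0.21/0.98 = 21.4%, about 86 of 400; 78.6% without PTSD.

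**3. How far the pooled effect could shrink.** Let s be the PTSD share, d the effect in men with PTSD, and r the effect in other men as a fraction of d. Pooled effect = d × [s + (1 - s) × r]. The documents supply neither r nor a d specific to men with PTSD, so both are assumptions.

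| d in men with PTSD | r | Pooled d | Power at N = 400 |
|---|---|---|---|
| 0.60 | 0 | 0.13-0.20 | .25-.53 |
| 0.60 | 0.5 | 0.36-0.40 | .95-.98 |
| 0.30 | 0 | 0.06-0.10 | .10-.17 |
| 0.30 | 0.5 | 0.18-0.20 | .44-.52 |
| 0.30 | 1 | 0.30 | .85 |

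The result depends almost wholly on the assumed d and r.

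**4. Gain from baseline adjustment.** If the baseline score correlates ρ with the outcome, the residual SD falls by √(1 - ρ²). With ρ = 0.5 (assumed) and an unadjusted d of 0.30, the effective d is 0.30/√0.75 = 0.346 and power at 400 is .93, against .85. With ρ = 0.3 it is 0.30/√0.91 = 0.314, power .88. With ρ = 0.7 it is 0.30/√0.51 = 0.420, power .99.

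**5. Precision of an interaction.** As a guide, split at PTSD status with 1:1 allocation in each part. The SE of the difference between the two arm effects, in SD units, is √(4/n1 + 4/n2).
- 86 and 314 men: √(4/86 + 4/314) = 0.243.
- 135 and 265 men: √(4/135 + 4/265) = 0.211.

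For comparison, the main-effect SE is √(4/200 + 4/200)/2 = 0.10. Two-sided power at .05 is about .23-.29 for a differential of 0.30 SD and .69-.81 for 0.60 SD, before loss to follow-up.

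**The case against.** The strongest reply is that absence of PTSD is not absence of trauma symptoms. Sections 1.1 and 5.0 count depression, anxiety and substance abuse as trauma symptoms, and section 2.0 lists more. No prevalence of any symptom is given, so the share of men outside TARGET's described population is unknown and may be well below two thirds. This stands.

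Three further points also stand:
- Low symptoms in custody do not imply a zero arm difference. Sections 2.0 and 4.1 describe reentry as a time of heightened stress and the program as support through it, so preventing worsening after release would show as a between-arm effect. The limited-room argument is strongest for the PCL-5. It does not carry over automatically to coping, impulsivity or aggression.
- The 21% and the 62-98% come from different samples, and neither is specific to moderate- to high-risk men aged 18-35.
- The SAP says its effect size comes from a similar population, so it may already average over mixed symptom levels.

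A reader might therefore infer that pooling dilutes the primary result, or that most men had nothing to improve. The documents support neither. The power figures above run from .10 to .98 on assumptions the documents do not supply, and no floor is demonstrated.

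The covariate list is given as examples, so the SAP does not rule out a baseline score. But it does not commit to one either.

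**Conclusion.** The mismatch between TARGET's described population and the entry rule is in the text, and the protocol does not explain it. Roughly 66-79% of enrolled men may not have PTSD, provided that the two background rates apply to this sample and that all PTSD cases pass the screen. Two thirds or more is true only to rounding at the low end.

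The pooled contrast remains a valid estimate for men selected on exposure, so the primary result is not invalidated. The defect is narrower: without a named baseline symptom covariate or any planned estimate of effect modification, a null PCL-5 result would be hard to interpret, and available precision may be left unused. The size of any loss cannot be fixed from the documents.

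**What to change.** Leave eligibility, randomisation and the overall comparison as they are. In the SAP:

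1. Name the baseline value of each mechanism score (PCL-5 for the PTSD outcome) as a covariate in that outcome's ANCOVA. The data are already collected, so the cost is wording and, at most, one residual degree of freedom per model.
2. Prespecify one secondary analysis: an arm-by-baseline-PCL-5 interaction, with baseline PCL-5 kept continuous, for the PCL-5 outcome only. Report the estimate with its confidence interval.
3. Word the overall conclusion as applying to men selected on trauma exposure, not on current symptoms.

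The downside is in item 2. With an SE more than twice that of the main effect, the interaction can show a large differential but will often miss a moderate one, and a non-significant result must not be read as a uniform effect. For that reason it should be labelled secondary and not confirmatory. Interactions on every mechanism would multiply imprecise estimates and are not needed; nor is stratified randomisation by PCL-5.

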5.0 Procedures Involved*

6.1 The proposed 5-year study is a two-armed 1:1 Randomized Controlled Trial (RCT) implementing and evaluating the effectiveness of a comprehensive trauma-based reentry program for young men releasing from prison to the community evaluated as moderate- to high- risk for recidivism. A total of 400 18-35 year old males releasing to one of the four participating urban and rural counties in Florida (Columbia, Duval, Leon, and Suwanee) will be randomly assigned to participate in the comprehensive trauma-based reentry program or a treatment-as-usual (TAU) control group. Participants in the comprehensive trauma-based reentry program will participate in up to four group sessions while incarcerated and up to 15 group sessions in the community after release. The effectiveness of the comprehensive trauma-based reentry program for 18-35 year old males will be evaluated on the following constructs: key mechanisms of change, community stability, and recidivism. Participants assigned to the treatment-as-usual control group will remain eligible to participate in all reentry services they normally would have received.

The purpose of this study is to evaluate the impact of a comprehensive trauma-based reentry program for moderate- to high-risk young incarcerated males between the ages of 18-35 on post-release outcomes. We will assess changes in key mechanisms of change (i.e. mediators) as well as post-release outcomes. The key mechanisms of change include: trauma symptoms (PTSD, depression, anxiety, and substance abuse), coping, impulsivity, and aggression. Post-release outcomes include community stability (i.e., housing and employment), and recidivism (i.e., re-arrest and re-incarceration for technical violation or new crime; time to re-incarceration).

5.2 Research team members are trained interventionists in order to assess if there are adverse behaviors or thoughts during service delivery (treatment group) and during data collection interviews (all participants). All interviews are conducted one-on-one so the research team member can assess for adverse reaction to the data collection or treatment delivery.

5.3 Research team members have experience working with people with trauma histories. This is important so they can successfully assess if there are adverse behaviors or thoughts during service delivery (treatment group) and during data collection interviews (all participants). All interviews are conducted one-on-one so the research team member can assess for adverse reaction to the data collection or treatment delivery.

6.4 Data will be collected from participants during one-on-one interviews. Interviews will occur in a private space, where the conversation between the team member and individual cannot be

heard. Data will be recorded in RedCap computer software. Potential participants will complete 12 -count trauma checklist as a screener for assessing for presence of at least one LTE. Eligible participants will plan to release to one of our four Florida counties. Participants will be consented using a Florida State University IRB consent form. If the individual meets screening criteria and consents into the study, the research team member will complete the baseline interview.

All consented participants (treatment and control) will complete a series of interviews. Baseline interviews will occur immediately after consent and occur in prisons. Follow-up interviews will be conducted in the community and timepoints include (1) after the conclusion of the program period, (2) three months after the conclusion of the program period, and (3) nine months after the conclusion of the program period.

6.5 Measures were selected based on the quality of established psychometric evidence and use with criminal justice-involved or other at-risk populations.

- Risk Assessment. Spectrum is the assessment tool used by FDC that identifies risk factors for criminal behavior. Scores on Spectrum range 1-5. The assessment is given to individuals at intake, periodically throughout incarceration and then again under a year before they release and measures an individual's risk to recidivate.
- Trauma screener. A dichotomous Yes/No measure of 12 LTEs from the Trauma Assessment for Adults serves as the trauma screening tool. Participants are identified as eligible if they have experienced at least one LTE.
- Demographics. Age, race/ethnicity, marital status, level of education at release, age at first offense, number of prior incarcerations, most serious offense, and current sentence length will be collected from FDC administrative databases.
- Trauma. The 24-item Trauma History Questionnaire (THQ)⁷² was designed to assess LTEs among general, community, and clinical populations. Each item examines a specific traumatic experience under the categories of interpersonal violence, accidents and disasters, serious illness, traumatic loss, and criminal victimization. Participants indicate whether they experienced the event, and if so, they provide age at time of exposure and a brief description. The THQ operationalizes *Diagnostic and Statistical Manual of Mental Disorders, 5th edition (DSM-5)* criteria for LTEs. The THQ is a reliable measure of trauma exposure (3-month test-retest coefficients=.51-.91) and has strong convergent validity to other measures ($k=.61-1.00$).
- PTSD. The 20-item PTSD Checklist for DSM-5 (PCL-5)⁷³ will be used to assess PTSD symptoms at all interview timepoints. All items are scored on a 5-point Likert scale with 0= "not at all" and 4= "extremely". Scores above 33 indicate current incidence of PTSD. The PCL-5 has

strong reliability ($\alpha=.94$), test-retest correlations ($r=.82$), and has strong convergent validity and discriminant validity.

- **Depression.** The 11-item major depressive disorder subscale of the MINI International Neuropsychiatric Interview (MINI)⁷⁴ assesses current incidence of depression at all interview timepoints. Items are rated on a dichotomous Yes/No scale and follow *DSM-5* psychiatric guidelines. The MINI has strong interrater reliability and the kappa value for the major depressive disorder construct was adequate ($k=.72$).
- **Anxiety.** The 7-item anxiety subscale of the MINI assesses current anxiety disorders at all interview timepoints. Items are rated on a dichotomous Yes/No scale and follow psychiatric guidelines of the *DSM-5*. The MINI has strong interrater reliability and kappa values for anxiety disorder constructs were adequate ($k=.69-.84$).
- **Substance Use Disorder.** The 9-item substance use disorder subscale of the MINI assesses current incidence of substance use disorders at all interview timepoints. Items are rated on a dichotomous Yes/No scale and follow psychiatric guidelines of the *DSM-5*. The MINI has strong interrater reliability and the kappa value for the substance use disorder construct was adequate ($k=.74$).
- **Coping.** The 26-item Coping Self-Efficacy Scale⁷⁵ assesses self-efficacy and confidence in coping with stress at all interview timepoints. The C-SES is reliable and valid ($\alpha=.80-.91$).
- **Impulsivity.** The 30-item Barratt Impulsivity Scale (BIS)⁷⁶ assesses general impulsiveness at all interview timepoints on six first-order factors (attention, motor, self-control, cognitive complexity, perseverance, and cognitive instability impulsiveness) and three second-order factors (attentional, motor, and non-planning impulsiveness). The BIS was validated among community, clinical, and correctional samples ($\alpha=.79-.83$).
- **Aggression.** The 12-item Brief Aggression Questionnaire (BAQ)⁷⁷ evaluates physical aggression, verbal aggression, anger, and hostility at all interview timepoints. The BAQ has stable test-retest reliability and convergent validity with behavioral aggression measures.
- **Housing.** A 7-item housing measure will assess housing stability at all post-release timepoints. Sample items include, “Have you had to “double up” with friends or relatives?”, “Do you consider yourself homeless?”, and “Where are you living or staying now?”
- **Employment.** A 10-item employment measure assesses employment at all interview timepoints. During the initial in-prison interview, the participant will be asked to think about their employment six months prior to their current incarceration. In all post-release interviews, the participant will be asked to reflect on their employment in the previous three months. Sample items include, “What was your work situation right before your current incarceration/over the past 3 months]?” and “How long have you been at your current employment?”

- Recidivism. Recidivism data on arrests in Florida, incarceration in a Florida state prison, the number of days to arrest or incarceration, and the reason for incarceration (i.e., commission of new crime or violation of the terms of release) will be collected from FDC and Florida Department of Law Enforcement databases annually for three years.

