1.0 Objectives*

1.1 The purpose of this study is to evaluate the impact of a comprehensive trauma-based reentry program for moderate- to high-risk young incarcerated males between the ages of 18-35 on post-release outcomes. We will assess changes in key mechanisms of change (i.e. mediators) as well as post-release outcomes. The key mechanisms of change include: trauma symptoms (PTSD, depression, anxiety, and substance abuse), coping, impulsivity, and aggression. Post-release outcomes include community stability (i.e., housing and employment), and recidivism (i.e., re-arrest and re-incarceration for technical violation or new crime; time to re-incarceration).

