3.0 Study Endpoints*

3.1 Comprehensive trauma-based reentry program group members will show improvements in key mechanisms of change compared to TAU control group members.

3.2 Comprehensive trauma-based reentry program group members will have increased community stability compared to TAU control group members.

3.3 Hypothesis 3: Comprehensive trauma-based reentry program group members will have lower rates of recidivism and those who do recidivate will spend more days in the community prior to recidivism compared to TAU control group.

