6.0 Data and Specimen Banking*

- 6.1 Collected data is stored in REDCap, and research team members and data analysts have access to the system. Data is protected and HIPPA compliant. Data collected is the interview assessment data using the tools listed in 6.4 for the initial interview and the 3 follow-up interviews.

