- recidivism data, including dates and number of: rearrests resulting in a 48 hour stay, jail time, incarceration for a new conviction, re-incarceration from state prison for a new offense or technical violation, residential sanction facility;
- technical violations, including what the violation was and the result of violation;
- sanctions, including type, number received and reason for sanction;
- education level at admission and at release;
- employment status on admission and for those on parole;
- home plan upon release and housing status for those already released;
- program treatment referral or receipt by parole, including your need, services received and services completed

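### Housing, unlike employment, has no retrospective baseline: the randomised comparison stays unbiased, but a useful covariate and a description of balance are forgone

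*Protocol*

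**What the plan says.** Protocol section 1.0 defines community stability as housing and employment. The Study Summary makes it a secondary objective. Section 3.0 words the endpoint as a comparison of arms: program members "will have increased community stability compared to TAU control group members".

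On timing, section 5.0 (item 6.4) states: "Baseline interviews will occur immediately after consent and occur in prisons". Three community interviews follow. Item 6.5 then gives a schedule for each measure. PTSD, depression, anxiety, substance use, coping, impulsivity, aggression and employment are taken at every interview. Housing is the exception: "A 7-item housing measure will assess housing stability at all post-release timepoints".

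Employment cannot be observed in prison either, and the protocol deals with that directly: "During the initial in-prison interview, the participant will be asked to think about their employment six months prior to their current incarceration".

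Two other places touch on housing or on what is collected:
- Section 6.0: "Data collected is the interview assessment data using the tools listed in 6.4 for the initial interview and the 3 follow-up interviews".
- Section 18.3, among the administrative data: "home plan upon release and housing status for those already released".

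The SAP analyses housing and employment by ANCOVA, "controlling for the effects of one or more covariates". Its examples are race, other program participation and criminal history.

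**The concern.** A man's own earlier housing instability is a natural candidate to predict his housing after release, and it is fixed before randomisation. ANCOVA gains precision from covariates of this kind. The schedule collects a pre-incarceration value for employment but not for housing, although the two stand side by side in the same research question.

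Two things are at stake. The housing analysis may be less precise than it could be with the same 400 men. The report will also be unable to show how the arms compared on prior housing.

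For the other interview-measured outcomes, a baseline covariate could be added later by amending the SAP alone, because the data will exist. For housing, they will not have been collected before treatment.

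**Working it through.** **1. Is a pre-incarceration housing value collected anywhere?**

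| Source | What it gives | Prior housing? |
|---|---|---|
| Protocol 5.0, item 6.5, Housing | Seven items, post-release interviews only | No |
| Protocol 5.0, item 6.5, Employment | Retrospective baseline | Employment only |
| Protocol 6.0 | General statement about tools at the initial and follow-up interviews | Adds no housing item; does not override the housing-specific schedule |
| Protocol 18.3, home plan | A plan for release; date of recording not stated | No |
| Protocol 18.3, housing status | Status of men already released | No |

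The home plan is at best a partial proxy. Section 4.0 says the in-prison sessions include reentry planning. If the plan is recorded after those sessions begin, it may be affected by assignment.

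**2. The plan's own ANCOVA figure.** The SAP gives N = 352 for two groups, up to seven covariates, alpha .05, power .80 and an effect of .15. Using the noncentral F with df1 = 1, df2 = N − 2 − 7 and noncentrality f²N:
- With f = .15, N = 351, and power is .801 at 352 and .849 at 400. This agrees with the SAP's 352.
- With d = .15 as labelled (f = .075), N = 1,398, and power at 400 is .322.

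The label is a separate matter, and the present point does not depend on it.

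**3. What a baseline covariate would be worth.** Let r be the correlation of prior with post-release housing that remains after the other covariates. The documents give no value, so .1 to .5 is an assumption. Residual variance is multiplied by 1 − r², and 400 adjusted men are worth 400/(1 − r²) unadjusted men.

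| r | 1 − r² | 400/(1 − r²) | Gain |
|---|---|---|---|
| .1 | .99 | 404 | 1% |
| .2 | .96 | 417 | 4% |
| .3 | .91 | 440 | 10% |
| .5 | .75 | 533 | 33% |

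On the f = .15 reading, the noncentrality at N = 400 is .0225 × 400 = 9.00 without the covariate and 9.00/(1 − r²) with it. Power rises from .849 to .863 (r = .2), .880 (r = .3) or .933 (r = .5).

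**4. Chance imbalance.** With 200 men per arm, the difference between arms on a standardised prior-housing score has standard error √(2/200) = 0.10 SD, so its 95% range is about ±0.196 SD. At that limit the unadjusted housing contrast moves by 0.196 × r: 0.04 SD at r = .2, 0.06 at .3 and 0.10 at .5.

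As a proportion, if 15% to 30% of men were previously unstably housed (assumed), the 95% range is 1.96 × √(2p(1 − p)/200): ±7.0 points at p = .15 and ±9.0 points at p = .30. This is ordinary sampling variation, which the unadjusted standard error already covers. It is largely the same cost as in step 3 and should not be added to it.

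**The case against.** The strongest objection is that nothing in the planned test is wrong. Allocation is 1:1 randomised and the endpoint is a contrast between arms, not change from baseline. A reader might infer that, without baseline housing, the arms cannot be trusted to have started equal and the housing result is therefore suspect. The documents do not support that. Randomisation makes the arms comparable in expectation, and baseline employment, substance use and criminal history allow a partial check of balance and partial adjustment. This objection stands and limits the point to precision and description.

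Four further objections have force:
- **The gain may be small.** Sentence length varies, and prison time separates the two housing measurements. A correlation of .1 or .2 is plausible, and the gain is then only 1-4%.
- **The formula is approximate.** It treats housing as a continuous score. The protocol gives no scoring rule, and its sample items include a yes/no question and a question on current living place. It also ignores loss to follow-up.
- **The SAP names no baseline outcome value as a covariate for any outcome.** Collecting prior housing without naming it in the model would secure no gain.
- **Current housing has no useful meaning for a man in prison.** That explains the schedule but does not settle the matter, because employment has the same difficulty and the protocol resolves it by asking about the earlier period.

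A reader might also take the loss as irrecoverable. Prior housing is a historical fact and could be asked about later, but with longer recall, some men missing, and answers possibly influenced by assignment.

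**Conclusion.** The gap is real and its consequence is modest. Housing is one of the two components of a secondary objective, and no pre-incarceration housing history is listed anywhere, although employment has one. The protocol defines no composite or weighting, so housing should not be described as a fixed share of the endpoint.

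The loss is a potentially useful ANCOVA covariate and a baseline description. Neither validity nor the planned test is threatened. The size rests on the assumed correlation: 404 to 533 equivalent men instead of 400 for a remaining correlation of .1 to .5, with a continuous score and before dropout. The upper end should not be quoted without the lower. The change is worth making because it is cheap and baseline is the cleanest time to ask.

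**What to change.** - **Protocol section 5.0, item 6.5 (Housing).** Add to the in-prison baseline interview a version of the housing items reworded for the six months before the current incarceration, as is done for employment. The items cannot be reused as they stand, because some ask about the present, such as where the man is living now.
- **SAP, Key Mechanisms of Change and Community Stability.** Name this value as a covariate in the housing analysis, within the seven that the power calculation allows, and show it by arm in the baseline table.

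The cost is a few minutes in an interview that section 24.1 puts at 1.5 to 2 hours, plus small edits to the protocol, the REDCap form and the SAP. The downside is retrospective recall error, which the protocol already accepts for employment. No extra enrolment is needed.
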